**Figure 12-1: Schematic diagram of TB test results and study eligibility**

IGRA=interferon-gamma release assay; TB=tuberculosis

a IGRA retest must be done during the protocol-defined Screening window

b Subjects with LTBI may enter the study only after they have completed at least 8 weeks of appropriate prophylactic therapy and thereafter, will continue and complete the entire regimen.

### **12.3.1.1 Tuberculosis assessment by IGRA**

During conduct of the study, the TB assessment by IGRA (QuantiFERON TB test is recommended) will be performed as described in [Table 5–1](#), [Table 5–2](#), and [Table 5-3](#) for all subjects. The test results will be reported as positive, negative, or indeterminate. Positive and indeterminate TB test results must be reported as an AE and appropriately updated once the final diagnosis is known (eg, active TB, latent TB, or false positive TB test). UCB also recommends that a TB specialist be consulted where TB (latent or active) is suspected or if there are doubts regarding test results. If active TB is identified, subject must undergo appropriate study-specified withdrawal procedures. The retest during Screening must be done during the protocol-defined Screening window.

### **12.3.1.2 Chest x-ray for tuberculosis**

A plain posteroanterior chest x-ray must be performed in the Screening Period unless one has been performed within 3 months prior to the Screening Visit. The chest x-ray (or, if done, computed axial tomography of the chest) must be clear of signs of TB infection (previous or current) before first IMP administration. All chest imaging (particularly x-rays) should be available for review by the Investigator before randomization of the subject. The chest x-ray reading should be repeated if the TB test was confirmed positive. If the second read of the pretreatment chest x-ray is confirmed to be clear, the patient may be included in the study 8 weeks after the start of the TB prophylactic treatment. If the pretreatment chest x-ray is not available for a re-read, it should be repeated after notification to the radiologist that this patient is IGRA positive, and confirmed to be clear for signs of TB.

The chest imaging must be negative for any old or recent TB infection as determined by a qualified radiologist and/or pulmonary physician. Any new clinically significant findings post Baseline on chest x-ray must be documented in the source documents and the eCRF as an AE.

### **12.3.1.3 Tuberculosis questionnaire**

The questionnaire “Evaluation of signs and symptoms of tuberculosis” should be used as a source document. The questionnaire will be completed as described in [Table 5–1](#), [Table 5–2](#), and [Table 5-3](#). The questionnaire will assist with the identification of subjects who may require therapy for TB. A subject who answers “Yes” to the question “Has the subject been in close contact with an individual with active TB, or an individual who has recently been treated for TB?” at Screening is excluded. A “Yes” response to any of the other questions within the questionnaire at Screening should trigger further careful assessment to determine if subject has LTBI or active TB (see Exclusion Criterion #12, [Section 6.2](#)). A “Yes” response to any of the questions during the study should trigger further assessments to determine if the subject has either LTBI or active TB infection.

### **12.3.1.4 Tuberculosis management**

LTBI and active TB identified during study

During the study, subjects who develop evidence of LTBI or active TB must immediately stop further administration of IMP and will be referred to an appropriate TB specialist (pulmonologist or infectious disease specialist) for further evaluation. Evidence of LTBI is defined as subject’s IGRA test converts to positive or indeterminate (and confirmed indeterminate on repeat), or the subject’s questionnaire or history and physical indicates that TB infection or exposure may have

occurred. Evidence of active TB includes, in addition to the aforementioned tests, signs and symptoms of organ involvement. In either situation, the subject should be carefully assessed by a TB specialist for active TB. Subjects diagnosed with active TB must be withdrawn from the study and receive appropriate TB therapy.

If a TB specialist excludes an active TB infection the subject can proceed with the IMP no earlier than 4 weeks after the start of an appropriate prophylactic therapy.

Any presumptive diagnosis or diagnosis of a TB infection is a reportable event. Confirmed active TB must be reported as an SAE. The Investigator is to complete and submit the TB Follow-Up Form provided.

The subject should be transferred to the care of his/her physician and managed according to the best available standard of care. Subjects identified as having converted to active TB during the study must be withdrawn and scheduled to return for the PEOT Visit as soon as possible but no later than the next scheduled study visit and complete all PEOT Visit assessments.

The subject should be encouraged to complete a SFU Visit (20 weeks after the final dose of IMP).

If infection with NTMB is identified during the study, the same procedure as for active TB acquired during the study must be followed.

### **12.3.2 Pregnancy testing**

Pregnancy testing will consist of serum testing at the initial Screening. The pregnancy test will be urine at other visits, including at the OLE2 Screening Visit.

The Screening Visit serum pregnancy testing results must be negative and received and reviewed prior to randomization.

A negative urine pregnancy test result should be obtained immediately prior to each administration of IMP at the visits specified in [Table 5-1](#), [Table 5-2](#), and [Table 5-3](#). Pregnancy tests should be administered to all female subjects of childbearing potential, regardless of their use of birth control.

Subjects of childbearing potential should conduct a home pregnancy test every 4 weeks. Home pregnancy tests will be provided to participants for use at Weeks 60, 68, 76, 80, 88, 92, 100, 104, 112, 116, 124, 128, 136, 140, and at the OLE2 Weeks 4, 8, 16, 32, and 40. At weeks on which IMP dosing is scheduled (specified in [Table 5-1](#), [Table 5-2](#), and [Table 5-3](#)), a negative urine pregnancy test result should be obtained immediately prior to the administration of IMP. In the case of a positive pregnancy test result, IMP should not be administered and the site should be contacted.

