#### 5.2.4 OLE2 Period

Subjects enrolled as per Protocol Amendment #5.1 will be treated in the OLE Period until Week 136 (last dose of bimekizumab 320mg Q8W) and will be followed in a SFU Period for 20 weeks after attending the Week 144 Visit (see Section 5.2.3). After the implementation of Protocol Amendment #5.4 (addition of a 48-week treatment period, ie, OLE2 Period), subjects will be invited to continue or reinstate their treatment as per the following OLE2 Groups:

- OLE2 Group A: Subjects in the treatment phase of the OLE Period at the time of Protocol Amendment #5.4 implementation will attend the Week 144 Visit and directly roll over to the OLE2 Period. These subjects will continue receiving bimekizumab 320mg Q8W for 40 additional weeks, starting from the first treatment visit of the OLE2 Period (ie, Week 144/OLE2 Baseline Visit; the Week 144 Visit will coincide with the Week 144/OLE2 Baseline Visit and data collected at this visit will be used as baseline data for subjects entering the OLE2 Period).
- OLE2 Group B: Eligible subjects who have completed the Week 144 Visit and are in the SFU or have completed the SFU of the OLE Period at the time of Protocol Amendment #5.4 implementation, will reinstate their treatment in the OLE2 Period after having undergone Screening assessments during a 4-week OLE2 Screening Period. The first dose will be administered at the Week 144/OLE2 Baseline Visit and data collected at this visit will be used as baseline data for the OLE2 Period. Subjects in OLE2 Group B with an IGA score  $\geq 3$  at the Week 144/OLE2 Baseline Visit will be treated with bimekizumab Q4W for the first 16 weeks, and then will switch to bimekizumab 320mg Q8W. Subjects in OLE2 Group B with an IGA score  $< 3$  at the Week 144/OLE2 Baseline Visit will be treated with bimekizumab Q8W from the Week 144/OLE2 Baseline Visit.

During the OLE2 Period (Week 144/OLE2 Baseline to OLE2 Week 48), all subjects will attend study visits every 12 weeks. All subjects will be treated until OLE2 Week 40 (last dose of bimekizumab 320mg Q8W).

Following completion or early withdrawal from the OLE2 Period, subjects will undergo the SFU of the OLE2 Period (SFU2) and will return for the SFU2 Visit 20 weeks after the last dose of IMP administration.

The assessments to be performed at each visit of the OLE2 Period are presented in [Table 5-3](#).

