- d Only applicable for subjects who completed the SFU period; only new or modified medical history since completing SFU will be entered in eCRF.
- e The physical examination will be performed as per Section 12.3.5.
- f These tests are performed as part of Week 144 Visit (the Week 144 Visit coincides with the Week 144/OLE2 Baseline Visit for subjects in Group A, ie, direct enroller from OLE to OLE2 Period).
- g Vital signs (sitting systolic and diastolic blood pressure, pulse rate, and temperature) are to be measured prior to blood sampling, and prior to dosing, where applicable.
- h Urine pregnancy testing will be performed at all visits. Pregnancy test results must be negative prior to administering IMP. Home pregnancy test kits will be provided to participants for use between clinic visits.
- i The HIV test results will not be recorded in the eCRF.
- j All blood samples taken prior to dosing.
- k Collected only from subjects in the SFU.

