**Table 7-3: Dosing scheme, OLE2 Period**

| Dose Assignment                        | Visits/Week | OLE2 Period            |         |         |                       |          |                       |          |                       |          |    |    |    |
|--|-------------|------------------------|---------|---------|-----------------------|----------|-----------------------|----------|-----------------------|----------|----|----|----|
|  |             | Week 144/OLE2 Baseline | OLE2 W4 | OLE2 W8 | OLE2 W12 a | OLE2 W16 | OLE2 W24 b | OLE2 W32 | OLE2 W36 c | OLE2 W40 |    |    |    |
| Bimekizumab 320mg Q4W/Q8W d |             | C                      | H       | H       | C                     | H        | C                     | H        | C                     | H        | C  |    |    |
| Bimekizumab 320mg Q8W                  |             | ●●                     | ●●      | ●●      | ●●                    | ●●       | ●●                    | ●●       | ●●                    | ●●       | ●● | ●● | ●● |

C=Clinic; H=home; IGA=Investigator’s Global Assessment; IMP=investigational medicinal product; Q4W/Q8W=every 4 weeks for 16 weeks, followed by every 8 weeks; Q8W=every 8 weeks; OLE=Open Label Extension; W=week

Notes: A bimekizumab 160mg injection is depicted by a black circle (●).

a Subjects will receive kits for home administration 4 weeks later.

b Subjects will receive kits for home administration 8 weeks later.

c Subjects should NOT be dosed at this visit and will receive kits for home administration 4 weeks later.

d Q4W/Q8W IMP administration only applies to those subjects who have entered the OLE2 Period as part of Group B, and had an IGA  $\geq 3$  upon entry of OLE2 Period. These subjects will receive Q4W dosing for 16 weeks until OLE2 Week 16, then will change from Q4W to Q8W and will receive their next dose at the scheduled clinic visit OLE2 Week 24.

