## **7.7 Procedures for monitoring subject compliance**

During the double-blind Treatment Period (up to Week 44), investigational medicinal product will be administered in the clinic and compliance will be determined at the visit by study personnel. Drug accountability must be recorded on the Drug Accountability Form.

After Week 48, self-injection at home will be possible at the following weeks: Weeks 60, 68, 76, 80, 88, 92, 100, 104, 112, 116, 124, 128, 136, 140, and at the OLE2 Weeks 4, 8, 16, 32, and 40. Dates, body locations, kit numbers and time of self-injection will be captured using a home administration form. All used syringes will be disposed of by subjects/caregivers as determined by the Investigator in an acceptable disposal (sharps) container directly after the administration. The subjects/caregivers return the documentation together with any used/unused containers at the next scheduled clinic visit.

Completed home administration forms should be reviewed by the Investigator with the subject. If a subject is noncompliant with the study procedures or medications that may present a risk to the safety of the subject in the opinion of the Investigator, then the subject should be withdrawn as described in Section 6.5.

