### **8.3.4 Self-injection at home (Weeks 60, 68, 76, 80, 88, 92, 100, 104, 112, 116, 124, 128, 136, and 140)**

The subject's dosing interval will change from bimekizumab 320mg Q4W to bimekizumab 320mg Q8W at Week 64 or at the next scheduled clinic visit (ie, Week 72, Week 84, Week 96, Week 108, Week 120, or Week 132) after implementation of Protocol Amendment #5.1 if the subject has already completed the Week 64 visit.

Subjects receiving bimekizumab 320mg Q4W will be given the opportunity for self-injection of bimekizumab at home on the following weeks: Weeks 60, 68, 76, 80, 88, 92, 100, 104, 112, 116, 124, 128, 136, and 140. This only applies to those subjects who have not yet changed to bimekizumab 320mg Q8W.

Subjects receiving bimekizumab 320mg Q8W will be given the opportunity for self-injection of bimekizumab at home on the following weeks: Weeks 80, 88, 104, 112, 128, and 136.

Subjects of childbearing potential should conduct a home pregnancy test every 4 weeks. In case of a scheduled home self-injection the pregnancy test needs to be performed immediately prior to self-injecting bimekizumab at home. If the pregnancy test result is positive, IMP should not be administered and the site should be contacted.

- Adverse events will be captured spontaneously if the subject decides to visit the site to receive the bimekizumab administration.
- All used syringes will be disposed of by subjects/caregivers as determined by the Investigator in an acceptable disposal (sharps) container directly after the administration. The subjects/caregivers return the documentation together with any used/unused containers at the next scheduled clinic visit.

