**8.4.3 Self-injection at home (OLE2 Weeks 4, 8, 16, 32, and 40)**

Subjects receiving bimekizumab 320mg Q8W will be given the opportunity for self-injection of bimekizumab at home on the following weeks: OLE2 Weeks 8, 16, 32, and 40.

Subjects receiving bimekizumab 320mg Q4W/Q8W will be given the opportunity for self-injection of bimekizumab at home on the following weeks: OLE2 Weeks 4, 8, and 16. At OLE2 Week 16, subjects receiving bimekizumab 320mg Q4W/Q8W will switch to bimekizumab 320mg Q8W regimen and will be given the opportunity for self-injection of bimekizumab at home dosed at OLE2 Weeks 32 and 40.

Subjects of childbearing potential should conduct a home pregnancy test every 4 weeks. In case of a scheduled home self-injection the pregnancy test needs to be performed immediately prior to self-injecting bimekizumab at home. If the pregnancy test result is positive, IMP should not be administered and the site should be contacted.

Adverse events will be captured spontaneously if the subject decides to visit the site to receive the bimekizumab administration.

All used syringes will be disposed of by subjects/caregivers as determined by the Investigator in an acceptable disposal (sharps) container directly after the administration. The subjects/caregivers return the documentation together with any used/unused containers at the next scheduled clinic visit.

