#### **8.4.4 OLE2 Week 12, Week 24, and Week 36 Visits ( $\pm 14$ days relative to OLE2 Baseline)**

As depicted in Table 7-3, subjects receiving bimekizumab 320mg Q4W/Q8W should receive IMP at the OLE2 Week 12 Visit, and all subjects will receive kits for home administration 4 weeks later at OLE2 Week 16. All subjects will receive IMP administration at the OLE2 Week 24 Visit, and will receive kits for home administration 8 weeks later. At the OLE2 Week 36 Visit, subjects will not be dosed and will receive kits for home administration 4 weeks later at OLE2 Week 40.

The following procedures/assessments will be performed/recorded at every clinic visit prior to administration of IMP:

- Physical exam
- Vital signs (sitting systolic and diastolic BP, pulse rate, and body temperature) should be obtained prior to blood sampling
- Urine pregnancy test, for applicable subjects
- Tuberculosis questionnaire
- PASI
- Percentage of BSA
- IGA
- Patient symptoms (itch, pain, and scaling)
- PHQ-9
- eC-SSRS
- Concomitant medication
- AEs
- Contact IRT

The following will be additional assessments will be performed / recorded every 24 weeks (ie, OLE2 Weeks 24 and 48) prior to administration of IMP

- Collection of blood and urine samples for the following tests should be obtained prior to dosing:
  - Hematology and biochemistry

- 
- Urinalysis
  - DLQI

At the OLE2 Week 12 and Week 24 Visit, after completion of the above-mentioned procedures, administration of IMP will occur, preferably by self-injection under supervision of the site personnel.

Distribution of IMP and accountability activities for home administration to be performed as described in Section 7.2, Section 7.5, and Section 7.7. Home pregnancy tests will be provided for testing every 4 weeks as appropriate (Table 5-2 and Table 5-3).

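### The OLE2 home pregnancy test list in Section 12.3.2 omits Weeks 20, 28 and 44, against the section's own 4-weekly rule

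*Protocol*

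**What the plan says.** Section 12.3.2 sets a frequency and then a supply list. The frequency is the one repeated for OLE2 in Section 8.4.3: "Subjects of childbearing potential should conduct a home pregnancy test every 4 weeks". The supply list names 14 weeks of the first open-label extension (OLE, Weeks 60 to 140) and then continues "and at the OLE2 Weeks 4, 8, 16, 32, and 40. At weeks on which IMP dosing is scheduled".

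Other parts of the protocol bear on the same point:

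- Section 5.2.4 fixes the OLE2 clinic visits: "During the OLE2 Period (Week 144/OLE2 Baseline to OLE2 Week 48), all subjects will attend study visits every 12 weeks".
- Table 5-3, footnote h, calls for a urine test at all visits and adds: "Home pregnancy test kits will be provided to participants for use between clinic visits".
- Section 8.4.4, on the OLE2 Week 12, 24 and 36 visits, says: "Home pregnancy tests will be provided for testing every 4 weeks as appropriate (Table 5-2 and Table 5-3".
- Section 7.7 gives the OLE2 home-injection weeks, and they are the same five: "140, and at the OLE2 Weeks 4, 8, 16, 32, and 40. Dates, body locations, kit numbers and time of self-injection".

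**The concern.** The list in Section 12.3.2 is the only place that names OLE2 home-test weeks one by one, and it does not deliver the frequency stated in the sentence before it. It appears to have been filled with the home-injection weeks.

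That worked in the first extension. Section 8.3.4 sets the home-injection weeks for the 4-weekly regimen ("Subjects receiving bimekizumab 320mg Q4W will be given the opportunity for self-injection of bimekizumab at home on the following weeks: Weeks 60, 68" and onwards), and with the clinic visits they cover every fourth week. In OLE2 no regimen is 4-weekly after Week 16. Footnote d of Table 7-3 says that subjects restarted on 4-weekly dosing "then will change from Q4W to Q8W and will receive their next dose at the scheduled clinic visit OLE2 Week 24". From then on the home-injection weeks cannot fill a 4-weekly calendar, and all three omissions fall after Week 16.

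What is at stake is the timing of recognition. Section 12.1.4 ties withdrawal, notification of the sponsor and counselling to the moment a pregnancy is known, so a missed interim test delays all of these.

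**Working it through.** The check compares a 4-weekly calendar with the weeks that have either a clinic test or a listed home kit.

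**First extension (Weeks 48 to 144), as a control**
- Points on the calendar: (144 − 48)/4 + 1 = 25.
- Listed home weeks (12.3.2): 60, 68, 76, 80, 88, 92, 100, 104, 112, 116, 124, 128, 136, 140, which is 14.
- Clinic weeks (5.2.3): 48, 52, 56, 64, 72, 84, 96, 108, 120, 132, 144, which is 11.
- 14 + 11 = 25, with no point missed. The list reproduces the rule.

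**OLE2 (Baseline to Week 48)**
- Points after Baseline: 48/4 = 12.
- Clinic weeks after Baseline (5.2.4): 12, 24, 36, 48, which is 4.
- Home tests needed: 12 − 4 = 8, at Weeks 4, 8, 16, 20, 28, 32, 40 and 44.
- Home tests listed: 5, at Weeks 4, 8, 16, 32 and 40.
- Missing: 8 − 5 = 3, at Weeks 20, 28 and 44. Table 5-3 has no column for any of them.

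**Intervals if kits are supplied by the list**

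Tests fall at 0, 4, 8, 12, 16, 24, 32, 36, 40 and 48. Three intervals exceed 4 weeks:

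| Interval | Length | Test omitted |
|---|---|---|
| Weeks 16 to 24 | 8 weeks | Week 20 |
| Weeks 24 to 32 | 8 weeks | Week 28 |
| Weeks 40 to 48 | 8 weeks | Week 44 |

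Together these make up 3 × 8 = 24 of the 48 weeks. Recognition is delayed only if the pregnancy becomes detectable in the first half of such an interval, which is 3 × 4 = 12 of the 48 weeks. In the second half the next test is the same under either schedule.

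With the ±14-day windows at both ends, an 8-week interval can run from 8 − 4 = 4 to 8 + 4 = 12 weeks. A correct 4-week interval can run from 0 to 8 weeks by the same arithmetic, so the omission itself accounts for 4 weeks and the windows for the rest.

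**Doses**

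| Regimen | Dose weeks | Doses without a test |
|---|---|---|
| Q8W | 0, 8, 16, 24, 32, 40 | 0 of 6 |
| Q4W then Q8W | 0, 4, 8, 12, 16, 24, 32, 40 | 0 of 8 |

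**After adding Weeks 20, 28 and 44:** no nominal OLE2 interval exceeds 4 weeks.

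**The case against.** The strongest reply is that the rule already covers the gap. It opens the same paragraph of Section 12.3.2 and recurs in 8.4.3. Section 8.4.4 and footnote h of Table 5-3 promise kits on a 4-weekly or between-visit basis, and 8.4.4 governs the very visits at which the missing kits would be handed out. The list does not claim to be exclusive, and nothing tells a site to withhold a kit. This stands as a limit on the size of the problem. It does not remove it: those passages name no weeks, the table that 8.4.4 points to has no column for the three weeks, and the one explicit list disagrees with them.

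A second reply is that drug exposure does not change. A pregnancy detectable at Week 20 or 28 would be found by the required test before the Week 24 or 32 dose, and that dose would be withheld either way. This is correct. What is delayed is reporting and counselling, in subjects who must use highly effective contraception (Sections 6.1 and 6.4.3).

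Third, the protocol accepts a longer untested interval elsewhere. After the Week 48 test the next is at the second safety follow-up visit, 20 weeks after the final dose. For a last dose at Week 40 that is Week 60, which is 12 weeks later. This supports a low rating, but the 4-weekly rule at issue is the one stated for OLE2 itself.

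Finally, the agreement of the first extension's list with the rule does not prove that Weeks 20, 28 and 44 were meant to be named, because both lists equal the home-injection weeks. That too is fair. The point rests on the 4-weekly rule; the comparison only explains how the gap probably arose.

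**Conclusion.** The concern holds as a minor inconsistency in a safety-monitoring instruction. The OLE2 list leaves out 3 of the 8 home tests that the section's own rule requires. The effect depends on how a site works: none if it follows the rule; three nominal 8-week intervals, and a delay in recognition of about 4 weeks for some pregnancies, if it supplies kits by the list. No scheduled dose goes without a required test, Week 44 matters least because it follows the last dose, few subjects would be affected, and no efficacy analysis changes. It is a change that could be made, not one on which the trial depends. The count assumes nominal visit weeks and a urine test at every OLE2 clinic visit, as footnote h of Table 5-3 states.

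**What to change.** In Section 12.3.2, replace the OLE2 weeks with 4, 8, 16, 20, 28, 32, 40 and 44. Dispense the Week 20 kit at the Week 12 visit, the Week 28 kit at the Week 24 visit and the Week 44 kit at the Week 36 visit. Leave the home-injection weeks in Sections 7.7 and 8.4.3 as they are, since those are correct for dosing. The cost is one line of protocol text and three more urine kits per applicable subject, with no added visits.
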